**Follow-up (2 hours)**

- All participants will complete outcome measure assessment after completion of the protocol, including re-administration of the Montreal Cognitive Assessment (**MoCA**), Movement Disorder Society-Sponsored Revision of the Unified Parkinson's Disease Rating Scale(**MDS-UPDRS**), 6-minute walk test (**6MWT**), mini-Balance Evaluation Systems Test (**Mini-BESTest**), Functional Gait Assessment (**FGA**), the modified Clinical Test of Sensory Integration and Balance (**mCTSIB**), Delis-Kaplan Executive Functioning System (**DKEFS**), Digit span test (DST), Digit symbol substitution test (DSST), Flanker test, **PROMIS-NeuroQOL**, the Short Form-36 (**SF-36**)
- Prior to follow-up, enrolled participants will receive an email from the study coordinator outlining the requirements of the clinically defined "off" state.

*Participants will be compensated with a \$100 clincard at the conclusion of this visit.*

**Statistical Analysis:**

To assess feasibility, we will track recruitment rate, retention rate, adverse events, and compliance. We will obtain patient feedback to gather insight about the acceptability and usability of this intervention. We will perform paired t-tests to compare the mean outcome measure values of the treatment and control groups to estimate effect size.

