**NCT #:** **NCT05871151**

**Document date:** **7/31/2025**

**Patient Population:**

\*\*We will recruit, screen, and enroll up 20 subjects in this study.

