### **Randomization Protocol:**

- To ensure that randomization is blinded, we will use a computer-generated randomization sequence.
- After obtaining informed consent, we will randomize eligible participants into one of two groups.
  - GROUP 1: active taVNS + exercise (details provided below)
  - GROUP 2: non-active taVNS + exercise (details provided below)

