### **Treatment Protocol:**

## **Initial Assessment (2 hours)**

\*\*Prior to the Initial Assessment, enrolled participants will receive an email from the study coordinator outlining the requirements of the clinically defined "off" state.

Outcome Measures: At the first study visit, Outcome Measure (OM) assessment will be conducted for ALL participants. Outcome measures (all previously validated in PD) will include the following:

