#### **Treatment (over the course of 4-6 weeks, 1 hour sessions, up to 3 sessions/week)**

- During treatment clinic visits, participants who are randomized into the **active taVNS + exercise** group will receive 15 minutes of active taVNS prior to treatment.
- Participants who are randomized into the **non-active taVNS + exercise** group will receive 0 mA of current for 15 minutes prior to treatment.
- To implement the non-active condition, participants will still undergo the same electrode placement procedure as those in the active taVNS group, with the electrodes placed in the ears. However, the taVNS device will be set to a 0 mA (no stimulation) during the non-active condition. Participants will be informed prior to the stimulation that they may or may not feel anything during the session, and that just because they do not feel anything does not mean that they are not receiving stimulation.

- All participants will be guided through low intensity, high amplitude exercises led by a trained exercise specialist.
- The exercise intervention proposed involves the supervision of a trained exercise specialist at all times during the treatment session
- The use of a gait belt will further ensure the participant's safety by providing additional support and stability during exercise
- The proposed exercise intervention will be conducted by a trained exercise specialist who has expertise in assessing and managing potential risks associated with exercise interventions. This will ensure that the intervention is safe for the participant and will minimize the risk of injury or adverse events
- After each treatment session, participants will be asked post-intervention questions to evaluate potential side effects of the taVNS treatment and exercise (see below):
  - 1. Since our last session, have you experienced any unusual physical symptoms such as dizziness, fatigue, muscle soreness, shortness of breath, or heart palpitations?
  - 2. Have you experienced any unusual discomfort or pain in the ear where the taVNS device was applied?
  - 3. Have you noticed any changes in your skin around the area where the taVNS device was applied, such as redness, swelling, or rash?
  - 4. Have you felt any changes in your mood, like feeling more anxious, depressed, or irritable since the last session?
  - 5. Have you noticed any changes in your ability to concentrate or remember things?

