### Re-Assessment (2 hours)

\*\*Prior to the re-assessment, enrolled participants will receive an email from the study coordinator outlining the requirements of the clinically defined "off" state.

- All participants will complete outcome measure assessment after completion of the protocol, including re-administration of the Montreal Cognitive Assessment (**MoCA**), Movement Disorder Society-Sponsored Revision of the Unified Parkinson's Disease Rating Scale(**MDS-UPDRS**), 6-minute walk test (**6MWT**), mini-Balance Evaluation Systems Test (**Mini-BESTest**), Functional Gait Assessment (**FGA**), the modified Clinical Test of Sensory Integration and Balance (**mCTSIB**), Delis-Kaplan Executive Functioning System (**DKEFS**), Digit span test (DST), Digit symbol substitution test (DSST), Flanker test, **PROMIS-NeuroQOL**, the Short Form-36 (**SF-36**)
- Additionally, participants will complete a qualitative interview to assess tolerability and feasibility of the treatment provided in this study. The interview will be recorded and transcribed on a HIPPA compliant platform and will be stored in a secure database. Audio and transcription will be analyzed at the conclusion of the study.
- Participants will be asked to answer a series of questions about the tolerability of the taVNS treatment & exercise intervention via a RedCap survey.

*Participants will be compensated with a \$100 clincard at the conclusion of this visit.*

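### The only comparative analysis is a paired t-test between two independently randomised groups, which have no pairs across arms

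*Combined protocol and SAP*

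**What the plan says.** The Statistical Analysis section first lists feasibility tracking ("we will track recruitment rate, retention rate, adverse events, and compliance") and patient feedback. Its one comparative sentence is "We will perform paired t-tests to compare the mean outcome measure values of the treatment and control groups to estimate effect size".

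The Randomization Protocol says "After obtaining informed consent, we will randomize eligible participants into one of two groups". One group receives active taVNS with exercise and the other non-active taVNS with exercise. A computer-generated sequence is mentioned, but no allocation ratio, blocking, matching or crossover.

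The sample size is a ceiling without a calculation: "We will recruit, screen, and enroll up 20 subjects in this study".

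Outcomes are collected three times. At the Initial Assessment, "At the first study visit, Outcome Measure (OM) assessment will be conducted for ALL participants". At the Re-Assessment, "All participants will complete outcome measure assessment after completion of the protocol", and the Follow-up section describes a further round in the same terms. The Statistical Analysis section does not say which visit, or which change between visits, is analysed, or how the effect size is standardised.

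**The concern.** A paired t-test needs a natural link between each observation in one sample and one observation in the other. This design has no such link between arms. The sentence can be read in two ways, and neither gives a sound treatment comparison.

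- **Literal reading, paired across arms.** Pairs would have to be invented. If arm sizes differ, by allocation or dropout, some participants must be discarded. If they are equal, the raw mean difference is the same under every pairing, but the standard error, confidence interval, p-value and any effect size based on the SD of paired differences depend on an arbitrary ordering.
- **Pre-post reading, paired within each arm.** The test is then valid for change within an arm but does not compare the arms. The Treatment section says "All participants will be guided through low intensity, high amplitude exercises led by a trained exercise specialist", so change in either arm mixes exercise, practice on repeated tests and time. The paired effect size also depends on the pre-post correlation.

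The sentence gives effect-size estimation as its purpose. That estimate is the main comparative output this pilot could hand to a later trial.

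**Working it through.** The plan states no power, significance level, target effect, SD or dropout, so it has no figure to reproduce. All numbers below are illustrations.

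**Inputs.** From the documents: at most 20 participants, two parallel groups. Assumed: the full 20, a 10:10 split where stated, normal outcomes, SD = 1, two-sided 5% level, and the retention rates and correlations shown.

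**1. Precision with equal arms and complete data.** The standard error of the mean difference is √(2/10) = 0.447 SD.

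- Independent groups, 18 df: 2.101 × 0.447 = 0.94 SD half-width.
- Arbitrary pairing, 9 df, typical case: 2.262 × 0.447 = 1.01 SD half-width.

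The typical interval is thus about 8% wider (1.01/0.94).

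**2. Dependence on the pairing.** Simulated data sets of 10 per arm were rescaled so that the observed pooled-SD difference was exactly 0.5, and each was re-paired at random 500 times. The table averages the percentiles over data sets.

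| Quantity | 2.5% | Median | 97.5% |
|---|---|---|---|
| Paired 95% CI half-width (SD) | 0.65 | 1.01 | 1.28 |
| Effect size from paired differences | 0.28 | 0.35 | 0.56 |

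The median effect size matches theory: 0.5/√2 = 0.35.

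For scale, the correct 95% confidence interval for an observed 0.5 at 10 per arm (noncentral t, 18 df) is −0.40 to 1.38. Sampling error exceeds the spread due to pairing.

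**3. Can the test use everyone?**

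- Fixed 10:10 allocation, completers independent Binomial(10, r) in each arm:

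| Assumed retention r | P(unequal completers) | Mean number unpaired |
|---|---|---|
| 0.95 | 0.54 | 0.7 |
| 0.90 | 0.69 | 1.0 |
| 0.85 | 0.75 | 1.2 |
| 0.80 | 0.78 | 1.4 |

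- Simple randomisation of 20, which the plan neither states nor excludes: P(10:10) = C(20,10)/2²⁰ = 0.176, so P(unequal) = 0.82. The mean absolute difference in arm size is 20 × 0.176 = 3.5.

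**4. Within-arm reading.** With equal SDs at both visits, the paired effect size is d/√(2(1 − ρ)), where ρ is the pre-post correlation. For a true change of d = 0.5 SD:

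- ρ = 0.5: 0.5/√1.0 = 0.50
- ρ = 0.8: 0.5/√0.4 = 0.79
- ρ = 0.9: 0.5/√0.2 = 1.12

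The same change more than doubles on this scale as the correlation rises, and none of these values is a between-group effect.

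**The case against.** The strongest reply has four parts.

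**The cost is modest.** If pairs were fixed without regard to outcomes, for example by enrolment order, the test would keep its nominal level: simulation at 10 per arm gave a type I error of 5.0%. The raw mean difference is unchanged, and the typical interval is only about 8% wider. This is correct. Numerically the loss is degrees of freedom (18 to 9), plus anyone left unpaired. But the plan gives no pairing rule, so the reported interval and any paired effect size could not be reproduced from it.

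**It may be a wording slip.** With repeated visits, within-arm pre-post tests may have been meant. That is plausible, but the sentence names a comparison of treatment with control, and within-arm tests do not supply one.

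**The numbers rest on assumptions.** The 82% figure needs simple randomisation, and 20 is a ceiling that screening exclusions may reduce. Both points stand, so the figures are illustrations. That no cross-arm pairs exist needs no assumption.

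**This is a feasibility study.** No hypothesis test or power is claimed, and the feasibility measures do not depend on this sentence. That limits the reach of the point but does not remove it, because estimating effect size is the sentence's own stated aim. The unstated visit and effect-size scale are lesser gaps that would not carry the point alone.

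**Conclusion.** The concern holds and should be corrected before analysis. The named test does not fit a parallel-group design, and nothing elsewhere in the document repairs it.

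The case rests on validity and reproducibility, not on lost power. Depending on the reading, the analysis drops participants when arm sizes differ, gives an interval and p-value that change with row order, or does not estimate the effect of active against non-active taVNS. An effect size taken from cross-arm paired differences would typically be about 0.71 (1/√2) times the usual standardised difference. One taken from within-arm change would vary with the pre-post correlation. Either could mislead the planning of a later trial.

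The raw mean difference with equal arms and complete data is not affected. The sizes given depend on the assumed 20 participants, equal SDs, normality, retention and correlations, none of which the document supplies.

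**What to change.** Replace the comparative sentence with wording such as:

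> For each outcome measured at that visit, values at re-assessment (and separately at follow-up) will be compared between the randomised groups with an independent-groups analysis. The mean difference and Hedges g, standardised by the pooled between-participant SD, will be reported with 95% confidence intervals. Paired tests will be used only to describe change within each group.

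State which of the two visits is the main one. The restriction to outcomes measured at that visit matters because the 10-Meter Walk Test is in the Initial Assessment battery but is not named in the Re-Assessment or Follow-up lists.

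An optional improvement is to make the comparison an ANCOVA with the Initial Assessment value as covariate. The expected half-width is approximately t(0.975, 17) × √0.2 × √(1 − ρ²) × √(1 + 1/16), where ρ is now the baseline-outcome correlation:

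- ρ = 0.5: 2.110 × 0.447 × 0.866 × 1.031 = 0.84 SD
- ρ = 0.8: 2.110 × 0.447 × 0.600 × 1.031 = 0.58 SD

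The unadjusted half-width is 0.94 SD. Both correlations are assumed.

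The cost is a few sentences of analysis text, with no new data, visits or participants. ANCOVA uses one further degree of freedom per outcome.

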### **Cognitive Assessments:**

1. Delis-Kaplan Executive Functioning System (DKEFS) Trails Test - The Delis-Kaplan Executive Function System (DKEFS) is a neuropsychological test battery that assesses various aspects of executive function, including cognitive flexibility, inhibition, and problem-solving. The trails test assesses visual attention and task switching. Participants will be asked to draw lines connecting numbers and letters in sequential order as quickly and accurately as possible.
2. Delis-Kaplan Executive Functioning System (DKEFS) Color Word Interference Test - The Color Word Interference test assesses selective attention and response inhibition. Participants will be asked to name the ink color of printed words while inhibiting automatic reading of the word itself.
3. Delis-Kaplan Executive Functioning System (DKEFS) Verbal Fluency Test - the Verbal Fluency Test assesses language-based executive function. Participants will be asked to generate as many words as possible within a given category (e.g., animals) or starting with a specific letter. These tests are commonly used in clinical settings to assess executive function and may help detect potential cognitive impairments or changes in cognitive function over time.
4. Digit Span Memory Test (DSMT) - The Digit Span Memory Test is a neuropsychological test that assesses working memory. Participants will be presented with a series of numbers and asked to repeat them back in the same order (Digit Span Forward) or in reverse order (Digit Span Backward). The test takes approximately 5-10 minutes to complete
5. Digit Symbol Substitution Test (DSST) - The Digit Symbol Substitution Test (DSST) is a neuropsychological test that assesses cognitive processing speed and attention. Participants will be presented with a series of symbols paired with digits and asked to match as many symbols to their corresponding digits as possible within a set time limit. The test takes approximately 5-10 minutes to complete.
6. MoCA - The Montreal Cognitive Assessment (MoCA) is a brief screening test that assesses various cognitive domains, including attention and concentration, executive functions, memory, language, visuoconstructional skills, conceptual thinking, calculations, and orientations. The MoCA is used to detect mild cognitive impairment (MCI), a condition that can precede the onset of dementia and monitor changes in cognitive function over time.

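### No lead clinical outcome or visit is named for the group t-tests: up to 28 instrument-level comparisons are possible, so isolated p-values, or an effect singled out for its size, would mislead

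*Combined protocol and SAP*

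**What the plan says.** The Statistical Analysis section has three sentences. It begins with feasibility: "To assess feasibility, we will track recruitment rate, retention rate, adverse events, and compliance". Patient feedback on acceptability and usability follows. The clinical outcomes come last: "We will perform paired t-tests to compare the mean outcome measure values of the treatment and control groups to estimate effect size".

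The outcomes are defined elsewhere. The Initial Assessment section introduces the battery with "Outcome measures (all previously validated in PD) will include the following" and then lists physical tests, cognitive tests and questionnaires. The Re-Assessment section repeats 12 named instruments, ending with "Digit span test (DST), Digit symbol substitution test (DSST), Flanker test, PROMIS-NeuroQOL, the Short Form-36 (SF-36". The Follow-up section repeats the same 12 under the statement "All participants will complete outcome measure assessment after completion of the protocol".

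On size and design, the plan says "We will recruit, screen, and enroll up 20 subjects in this study" and "we will randomize eligible participants into one of two groups". No section states an alpha level, an allocation ratio, a lead clinical outcome, the visit or contrast to be tested, or how several results will be read together.

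**The concern.** The stated purpose of the t-tests is to estimate an effect size, but the plan does not say which one. A reader of the results could face a dozen to more than two dozen group comparisons of equal standing, each with a p-value and a standardised difference, from about 20 people.

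Two things are at stake. First, if nominal p-values are read at a conventional level, an isolated small one is fairly likely even if active taVNS adds nothing to exercise. Second, if one estimate is later quoted because it is the largest, it is biased upward, and a later trial planned on it would be too small. Naming the estimate of interest before the data are seen removes both problems. Naming it afterwards does not.

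**Working it through.** **No figure to reproduce.** The plan gives no alpha, power or sample-size calculation.

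**Inputs from the documents**
- Enrolment of up to 20 (Patient Population) in two randomised groups (Randomization Protocol).
- Instruments at each later visit: MoCA, MDS-UPDRS, 6MWT, Mini-BESTest, FGA, mCTSIB, DKEFS, digit span, DSST, Flanker, NeuroQOL and SF-36, which makes 12.
- DKEFS consists of three tests under Cognitive Assessments, the first being "Delis-Kaplan Executive Functioning System (DKEFS) Trails Test", with Color Word Interference and Verbal Fluency after it. Splitting it gives 12 − 1 + 3 = 14.
- The 10-Meter Walk Test appears in the baseline list only, so it is not counted.

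**Assumptions, not in the documents**
- Equal split, 20 / 2 = 10 per arm, with no dropout.
- Two-sided 0.05, unpaired t-tests, normal outcomes, no true effect.
- Correlation from 0 up to 0.7 between outcomes and 0.8 between visits.

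**Count of comparisons**
- Both visits, DKEFS split: 14 × 2 = 28.
- Both visits, DKEFS as one: 12 × 2 = 24.
- One visit: 14 or 12.
- Sub-scores could raise any of these. Flanker alone yields reaction time and accuracy.

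**Chance of at least one p<0.05 if the tests were independent: 1 − 0.95^k**
- k = 28: 1 − 0.95^28 = 0.762, with 28 × 0.05 = 1.4 expected.
- k = 24: 0.708, with 1.2 expected.
- k = 14: 0.512, with 0.7 expected.
- k = 12: 1 − 0.95^12 = 0.460, with 0.6 expected.

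**Correlated outcomes.** Independence is unrealistic for instruments repeated in the same people, so null trials were simulated (20,000 per row, 10 per arm). Here d is the difference in means divided by the pooled SD.

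| Correlation: outcomes / visits | 28 tests: any p<0.05 | 28 tests: mean largest \|d\| | 12 tests, one visit: any p<0.05 | 12 tests: mean largest \|d\| |
|---|---|---|---|---|
| 0 / 0 | 76% | 1.14 | 46% | 0.95 |
| 0.3 / 0.7 | 64% | 1.07 | 40% | 0.91 |
| 0.5 / 0.8 | 51% | 0.99 | 33% | 0.86 |
| 0.7 / 0.8 | 38% | 0.89 | 24% | 0.76 |

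The visit correlation does not affect the 12-test columns, which use a single visit.

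**Comparator.** For one outcome at one visit named in advance, the error rate is 5% and the mean |d| under no effect is about 0.37.

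**Sensitivity.** With 8 per arm and 28 tests, the mean largest |d| is 1.04 to 1.31, against about 0.42 for a single outcome.

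**Precision of one estimate.** With 10 per arm, a single test reaches p<0.05 only when |d| exceeds 2.101 × √(2/10) = 0.94. Naming a lead outcome removes selection bias but leaves the estimate imprecise, so an interval is needed.

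**The case against.** The strongest reply is that this is a small feasibility study. Feasibility measures come first, the t-tests last, and their stated purpose is estimation. Reporting effects across several measures without ranking them is a defensible exploratory choice, and if all estimates are reported, none is biased by selection. That stands, and it limits the point. It does not say which estimate is the one to carry forward, and the p-values that come with t-tests have no stated reading.

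A reader might infer several stronger things that the documents do not support:
- *That false positives will occur.* Under the assumptions above the chance is 38% to 76% for 28 tests, and the top figure needs full independence. No significance threshold is stated either.
- *That 28 is a minimum.* The plan does not say which visits or scores will be tested. One visit with DKEFS as one instrument gives 12, while sub-scores could take the count past 28.
- *That the reported effect size will be inflated.* This follows only if the largest estimate is singled out. The plan does not say it will be, or that any estimate will be used to size a later trial.
- *That t-tests are the only planned analysis.* Feasibility tracking and patient feedback are also planned.

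The plan's word *paired* is a further difficulty. A paired test does not fit a comparison of two independent randomised groups. If before-after tests within each arm were meant, the contrast and the figures above would change. The sentence does, however, name the treatment and control groups as what is compared, so the unpaired reading is used here.

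**Conclusion.** The concern holds in a limited form. The plan compares the two groups on its outcome measures without naming a lead clinical outcome or visit, or saying how the results will be read together. Even the narrowest count of 12 leaves roughly a one-in-four chance or more of a nominal p<0.05 somewhere under no effect, well above the 5% of a single named comparison. With 28 comparisons, an effect selected for its size would average more than twice the null value of a pre-named one (0.89 / 0.37 = 2.4 at the high-correlation end).

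These sizes rest on the assumed equal split, alpha, unpaired test and correlation range, none of which the documents give. The gap itself, with no lead outcome, visit or reading rule, rests on no assumption.

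**What to change.** Before unblinded data are examined, revise the last sentence of the Statistical Analysis section as follows:
- Name one lead clinical outcome and one visit. The choice belongs to the investigators. MDS-UPDRS Part III at Re-Assessment is one candidate, because the off-state paragraph under Inclusion Criteria refers to change in cardinal motor symptoms. That paragraph relies on the whole physical and cognitive battery, so it does not settle the choice.
- Report the between-group difference and the standardised difference for that outcome with 95% CIs, using a method for independent groups in place of *paired*.
- Report all other instruments, and the other visit, descriptively with 95% CIs and no significance claims.
- State that an effect picked out for its size will not be used to size a later trial.
- Keep feasibility as the first-listed aim.

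The cost is a few sentences of text, with no added visits, participants or procedures. The downside is that isolated p<0.05 results on other instruments could not be presented as efficacy.

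### The between-arm comparison specifies no use of the baseline value, although every re-administered instrument is measured at the Initial Assessment

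*Combined protocol and SAP*

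**What the plan says.** The whole efficacy analysis is one sentence in the Statistical Analysis section, which plans paired t-tests to "compare the mean outcome measure values of the treatment and control groups to estimate effect size". It does not say which visit is analysed, whether the values are post-treatment values or changes, or whether a baseline value enters. ANCOVA, change from baseline and mixed models are mentioned nowhere in the document.

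The baseline data will exist. Under Initial Assessment: "At the first study visit, Outcome Measure (OM) assessment will be conducted for ALL participants". Under Re-Assessment: "All participants will complete outcome measure assessment after completion of the protocol", followed by the list of instruments given again; the Follow-up section repeats that list.

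On design, the plan will "enroll up 20 subjects in this study" (Patient Population). Under Randomization Protocol, "we will randomize eligible participants into one of two groups" and "we will use a computer-generated randomization sequence". No allocation ratio, stratification or other balancing on baseline is described.

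**The concern.** For most repeated measures, a participant's starting value predicts part of the later value. A comparison of group means that leaves the starting value out keeps that predictable part as noise. With about 10 participants per arm the noise is considerable, and nothing described in the randomisation limits how far the arms may differ at the start.

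At stake is the between-arm effect size, which is the only efficacy result the section promises. If it feeds the planning of a later trial, its precision matters.

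This point is separate from the use of a paired test on two independent arms. Replacing that test with a two-sample t-test would correct the pairing and still leave baseline unused.

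**Working it through.** The documents state no power, alpha, effect size, SD or sample-size derivation, so there is no figure of the plan's own to reproduce. The calculation below illustrates the size of the point.

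**Coverage of baseline.** The Re-Assessment and Follow-up lists name MoCA, MDS-UPDRS, 6MWT, Mini-BESTest, FGA, mCTSIB, DKEFS, digit span, DSST, Flanker, NeuroQOL and SF-36. All twelve are in the Initial Assessment battery. The 10MWT is measured at the Initial Assessment but is not in either later list, so it falls outside this point.

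**Inputs**
- Total N = 20, the stated maximum (Patient Population).
- Two arms (Randomization Protocol). Assumed: 1:1 allocation, so n = 10 per arm, with no dropout.
- Assumed: two-sided 95% intervals, results in units of the outcome SD, and the same SD at baseline and later.
- Assumed: baseline-outcome correlation r from 0.3 to 0.8. The documents give none.

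**Unadjusted comparison of post-treatment means**
- SE = sqrt(2/10) = 0.447 SD.
- 95% half-width = t(0.975, 18 df) × SE = 2.101 × 0.447 = 0.94 SD.

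**ANCOVA on baseline**
- SE = sqrt((1 − r²) × (2/10) × (1 + 1/(N − 4))). With N = 20 the last factor is 17/16, the price of estimating the slope.
- 95% half-width = t(0.975, 17 df) × SE = 2.110 × SE.
- Equivalent N = 20 divided by the ratio of the ANCOVA variance to the unadjusted variance.

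| r | ANCOVA SE | 95% half-width | Variance ratio | Equivalent N | Shift from a 0.5 SD imbalance (r × 0.5) |
|---|---|---|---|---|---|
| unadjusted | 0.447 | 0.94 | 1 | 20 | see rows below |
| 0.3 | 0.440 | 0.93 | 0.97 | 21 | 0.15 |
| 0.5 | 0.399 | 0.84 | 0.80 | 25 | 0.25 |
| 0.7 | 0.329 | 0.69 | 0.54 | 37 | 0.35 |
| 0.8 | 0.277 | 0.58 | 0.38 | 52 | 0.40 |

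The last column is the shift in the *unadjusted* estimate. A simulation of 40,000 trials gave ANCOVA SEs of 0.397 at r = 0.5 and 0.330 at r = 0.7, in agreement with the formula.

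**Break-even.** The variances are equal when (1 − r²) × 17/16 = 1, that is r² = 1/17, r = 0.24. Allowing for the lost degree of freedom, break-even is about 0.25. The worst case, r = 0, costs a factor sqrt(17/16) = 1.03 in the SE.

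**Chance imbalance.** The baseline difference between arms also has SD 0.447. The probability that it exceeds 0.5 SD in either direction is 2 × (1 − Φ(0.5/0.447)) = 0.26.

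**These are one quantity, not two.** The unadjusted variance of 0.2 splits into r² × 0.2, which comes from baseline imbalance, and (1 − r²) × 0.2, which does not. At r = 0.7 that is 0.098 + 0.102. ANCOVA removes the first part, less the 17/16 factor. The imbalance figures therefore show where the extra width comes from; they are not a further harm to add to it.

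**The case against.** The strongest reply is that the sentence is ambiguous. It says paired, and the only natural pairs in this design are a participant's own assessments before and after treatment. On that reading baseline is used. It stands that the text cannot be taken as a decision to discard baseline. But a pre/post test within each arm yields no between-arm effect size, while the sentence says the two groups are compared. A between-arm comparison of change scores is not stated either. It would have SE sqrt(2(1 − r) × 0.2), which is 0.529 at r = 0.3 and 0.447 at r = 0.5, so below r = 0.5 it is worse than comparing post-treatment means. None of these readings gives a baseline-adjusted between-arm estimate.

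The second reply is that this is a feasibility study. Recruitment, retention, adverse events, compliance and patient feedback are unaffected, and no hypothesis test or power is claimed. That stands and limits the consequence to a less precise effect size. It does not remove the case for an improvement that needs no new data.

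The third is that the benefit depends on r, which is unknown and will differ between motor, cognitive and questionnaire measures. This also stands. For the MoCA, r may be lowered because eligibility cuts off low scores.

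A reader might infer three stronger things that the documents do not support:
- **That the estimate is biased.** Allocation is randomised, so chance imbalance is error in the one realised estimate and is already inside the 0.94 SD half-width.
- **That a baseline imbalance carries over in full.** It carries over multiplied by r.
- **That adjustment must bring a large gain.** Near r = 0.3 it brings almost none.

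**Conclusion.** The point holds as a missing specification with a better method at hand: the plan compares group means and specifies no use of a baseline value that it collects for every re-administered instrument. At an assumed 10 per arm without dropout, adjustment would narrow the 95% half-width from 0.94 SD to between 0.93 SD (r = 0.3) and 0.58 SD (r = 0.8). The direction is firm for any r above about 0.25; the size rests entirely on the assumed r. Fewer participants or unequal arms would widen all these intervals. The consequence is an avoidably imprecise effect size for any instrument with a moderate or high r. The feasibility results do not depend on it.

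**What to change.** Replace the efficacy sentence with one along these lines: for each re-administered instrument at each post-treatment visit, the between-arm difference will be estimated by a linear model of the post-treatment value on assigned group and that instrument's Initial Assessment value, and reported with its 95% CI in the instrument's own units. A mixed model over Re-Assessment and Follow-up, with baseline as covariate, is an equally acceptable choice.

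If a standardised effect is also reported, state which SD is the divisor. For the MoCA, note that the baseline SD is truncated by screening, so dividing by it would inflate the standardised effect. This applies whichever cut-off is in force: Exclusion criteria gives below 20 and Screening & Informed Consent gives below 25/30, and those two sections need reconciling.

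The cost is the rewritten sentence and one degree of freedom per model. No new data, visits or participants are needed. Counting the three DKEFS tests separately there are 14 measures at two visits, so about 28 estimates before subscales. Adjustment does not change that number, and the results should be presented as estimates with intervals.
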